11.1.3 Methods for Evaluation of Measurable Disease

All measurements should be taken and recorded in metric notation using a ruler or calipers. All baseline evaluations should be performed as closely as possible to the beginning of treatment and never more than 4 weeks before the beginning of the treatment.

The same method of assessment and the same technique should be used to characterize each

identified and reported lesion at baseline and during follow-up. Imaging-based evaluation is preferred to evaluation by clinical examination unless the lesion(s) being followed cannot be imaged but are assessable by clinical exam.

Clinical lesions. Clinical lesions will only be considered measurable when they are superficial (e.g., skin nodules and palpable lymph nodes) and ≥ 10 mm diameter as assessed using calipers (e.g., skin nodules). In the case of skin lesions, documentation by color photography, including a ruler to estimate the size of the lesion, is recommended. In the case that skin lesions are followed, documentation of pathologic CR of that lesion will be made via biopsy in the event that a previously raised lesion becomes flat.

Chest x-ray. Lesions on chest x-ray are acceptable as measurable lesions when they are clearly defined and surrounded by aerated lung. However, CT is preferable.

Conventional CT and MRI. This guideline has defined measurability of lesions on CT scan based on the assumption that CT slice thickness is 5 mm or less. If CT scans have slice thickness greater than 5 mm, the minimum size for a measurable lesion should be twice the slice thickness. MRI is also acceptable in certain situations (e.g. for body scans).

Use of MRI remains a complex issue. MRI has excellent contrast, spatial, and temporal resolution; however, there are many image acquisition variables involved in MRI, which greatly impact image quality, lesion conspicuity, and measurement. Furthermore, the availability of MRI is variable globally. As with CT, if an MRI is performed, the technical specifications of the scanning sequences used should be optimized for the evaluation of the type and site of disease. Furthermore, as with CT, the modality used at follow-up should be the same as was used at baseline and the lesions should be measured/assessed on the same pulse sequence. It is beyond the scope of the RECIST guidelines to prescribe specific MRI pulse sequence parameters for all scanners, body parts, and diseases. Ideally, the same type of scanner should be used and the image acquisition protocol should be followed as closely as possible to prior scans. Body scans should be performed with breath-hold scanning techniques, if possible.

PET-CT. At present, the low dose or attenuation correction CT portion of a combined PET-CT is not always of optimal diagnostic CT quality for use with RECIST measurements. However, if the site can document that the CT performed as part of a PET-CT is of identical diagnostic quality to a diagnostic CT (with IV and oral contrast), then the CT portion of the PET-CT can be used for RECIST measurements and can be used interchangeably with conventional CT in accurately measuring cancer lesions over time. Note, however, that the PET portion of the CT introduces additional data which may bias an investigator if it is not routinely or serially performed.

Ultrasound. Ultrasound is not useful in assessment of lesion size and should not be used as a method of measurement. Ultrasound examinations cannot be reproduced in their entirety for independent review at a later date and, because they are operator dependent, it cannot be guaranteed that the same technique and measurements will be taken from one assessment to the next. If new lesions are identified by ultrasound in the course of the study, confirmation by CT or MRI is advised. If there is concern about radiation exposure at CT, MRI may be used instead of CT in selected instances.

Endoscopy, Laparoscopy. The utilization of these techniques for objective tumor evaluation is not advised. However, such techniques may be useful to confirm complete pathological response when biopsies are obtained or to determine relapse in trials where recurrence following complete response (CR) or surgical resection is an endpoint.

Tumor markers. Tumor markers alone cannot be used to assess response. If markers are initially above the upper normal limit, they must normalize for a patient to be considered in complete clinical response. Specific guidelines for both CA-125 response (in recurrent ovarian cancer) and PSA response (in recurrent prostate cancer) have been published [*JNCI* 96:487-488, 2004; *J Clin Oncol* 17, 3461-3467, 1999; *J Clin Oncol* 26:1148-1159, 2008]. In addition, the Gynecologic Cancer Intergroup has developed CA-125 progression criteria which are to be integrated with objective tumor assessment for use in first-line trials in ovarian cancer [*JNCI* 92:1534-1535, 2000].

Cytology, Histology. These techniques can be used to differentiate between partial responses (PR) and complete responses (CR) in rare cases (e.g., residual lesions in tumor types, such as germ cell tumors, where known residual benign tumors can remain).

The cytological confirmation of the neoplastic origin of any effusion that appears or worsens during treatment when the measurable tumor has met criteria for response or stable disease is mandatory to differentiate between response or stable disease (an effusion may be a side effect of the treatment) and progressive disease.

FDG-PET While FDG-PET response assessments need additional study, it is sometimes reasonable to incorporate the use of FDG-PET scanning to complement CT scanning in assessment of progression (particularly possible 'new' disease). New lesions on the basis of FDG-PET imaging can be identified according to the following algorithm:

- a. Negative FDG-PET at baseline, with a positive FDG-PET at follow-up is a sign of PD based on a new lesion.
- b. No FDG-PET at baseline and a positive FDG-PET at follow-up: If the positive FDG-PET at follow-up corresponds to a new site of disease confirmed by CT, this is PD. If the positive FDG-PET at follow-up is not confirmed as a new site of disease on CT, additional follow-up CT scans are needed to determine if there is truly progression occurring at that site (if so, the date of PD will be the date of the initial abnormal FDG-PET scan). If the positive FDG-PET at follow-up corresponds to a pre-existing site of disease on CT that is not progressing on the basis of the anatomic images, this is not PD.
- c. FDG-PET may be used to upgrade a response to a CR in a manner similar to a biopsy in cases where a residual radiographic abnormality is thought to represent fibrosis or scarring. The use of FDG-PET in this circumstance should be prospectively described in the protocol and supported by disease-specific medical literature for the indication. However, it must be acknowledged that both approaches may lead to false positive CR due to limitations of FDG-PET and biopsy resolution/sensitivity.

Note: A 'positive' FDG-PET scan lesion means one which is FDG avid with an uptake greater than twice that of the surrounding tissue on the attenuation corrected image.

11.1.4 Response Criteria

11.1.4.1 Evaluation of Target Lesions

Complete Response (CR): Disappearance of all target lesions. Any pathological lymph nodes (whether target or non-target) must have reduction in short axis to <10 mm.

Partial Response (PR): At least a 30% decrease in the sum of the diameters of target lesions, taking as reference the baseline sum diameters.

Progressive Disease (PD): At least a 20% increase in the sum of the diameters of target lesions, taking as reference the smallest sum on study (this includes the baseline sum if that is the smallest on study). In addition to the relative increase of 20%, the sum must also demonstrate an absolute increase of at least 5 mm. (Note: the appearance of one or more new lesions is also considered progressions).

Stable Disease (SD): Neither sufficient shrinkage to qualify for PR nor sufficient increase to qualify for PD, taking as reference the smallest sum diameters while on study.

11.1.4.2 Evaluation of Non-Target Lesions

Complete Response (CR): Disappearance of all non-target lesions and normalization of tumor marker level. All lymph nodes must be non-pathological in size (<10 mm short axis).

Note: If tumor markers are initially above the upper normal limit, they must normalize for a patient to be considered in complete clinical response.

Non-CR/Non-PD: Persistence of one or more non-target lesion(s) and/or maintenance of tumor marker level above the normal limits.

Progressive Disease (PD): Appearance of one or more new lesions and/or *unequivocal progression* of existing non-target lesions. *Unequivocal progression* should not normally trump target lesion status. It must be representative of overall disease status change, not a single lesion increase.

Although a clear progression of “non-target” lesions only is exceptional, the opinion of the treating physician should prevail in such circumstances, and the progression status should be confirmed at a later time by the review panel (or Principal Investigator).

11.1.4.3 Evaluation of Best Overall Response

The best overall response is the best response recorded from the start of the treatment until disease progression/recurrence (taking as reference for progressive disease the smallest measurements recorded since the treatment started). The patient's best response assignment will depend on the achievement of both measurement and confirmation criteria.

For Patients with Measurable Disease (i.e., Target Disease)

Target Lesions	Non-Target Lesions	New Lesions	Overall Response	Best Overall Response when Confirmation is Required*
CR	CR	No	CR	≥ 4 wks. Confirmation**
CR	Non-CR/Non-PD	No	PR	
CR	Not evaluated	No	PR	
PR	Non-CR/Non-PD/not evaluated	No	PR	≥ 4 wks. Confirmation**
SD	Non-CR/Non-PD/not evaluated	No	SD	Documented at least once ≥ 4 wks. from baseline**
PD	Any	Yes or No	PD	
Any	PD***	Yes or No	PD	no prior SD, PR or CR

Any	Any	Yes	PD	
* See RECIST 1.1 manuscript for further details on what is evidence of a new lesion.				
** Only for non-randomized trials with response as primary endpoint.				
*** In exceptional circumstances, unequivocal progression in non-target lesions may be accepted as disease progression.				
Note: Patients with a global deterioration of health status requiring discontinuation of treatment without objective evidence of disease progression at that time should be reported as " symptomatic deterioration. " Every effort should be made to document the objective progression even after discontinuation of treatment.				

For Patients with Non-Measurable Disease (*i.e.*, Non-Target Disease)

Non-Target Lesions	New Lesions	Overall Response
CR	No	CR
Non-CR/non-PD	No	Non-CR/non-PD*
Not all evaluated	No	not evaluated
Unequivocal PD	Yes or No	PD
Any	Yes	PD
* 'Non-CR/non-PD' is preferred over 'stable disease' for non-target disease since SD is increasingly used as an endpoint for assessment of efficacy in some trials so to assign this category when no lesions can be measured is not advised		

11.1.5 Duration of Response

Duration of overall response: The duration of overall response is measured from the time measurement criteria are met for CR or PR (whichever is first recorded) until the first date that recurrent or progressive disease is objectively documented (taking as reference for progressive disease the smallest measurements recorded since the treatment started).

The duration of overall CR is measured from the time measurement criteria are first met for CR until the first date that progressive disease is objectively documented.

Duration of stable disease: Stable disease is measured from the start of the treatment until the criteria for progression are met, taking as reference the smallest measurements recorded since the treatment started, including the baseline measurements.

11.1.6 Progression-Free Survival

PFS is defined as the duration of time from start of treatment to time of progression or death, whichever occurs first.

12. DATA REPORTING / REGULATORY REQUIREMENTS

Adverse event lists, guidelines, and instructions for AE reporting can be found in Section 7.0 (Adverse Events: List and Reporting Requirements).

12.1 Data Reporting

12.1.1 Method

The ODQ will collect, manage, and perform quality checks on the data for this study.

12.1.2 Responsibility for Data Submission

Investigative sites within DF/HCC or DF/PCC are responsible for submitting data and/or data forms to ODQ according to the schedule set by the ODQ.

12.2 Data Safety Monitoring

The DF/HCC Data and Safety Monitoring Committee (DSMC) will review and monitor toxicity and accrual data from this study. The committee is composed of clinical specialists with experience in oncology and who have no direct relationship with the study. Information that raises any questions about participant safety will be addressed with the Overall PI and study team.

The DSMC will review each protocol up to four times a year or more often if required to review toxicity and accrual data. Information to be provided to the committee may include: up-to-date participant accrual; current dose level information; DLT information; all grade 2 or higher unexpected adverse events that have been reported; summary of all deaths occurring with 30 days of intervention for Phase I or II protocols; for gene therapy protocols, summary of all deaths while being treated and during active follow-up; any response information; audit results, and a summary provided by the study team. Other information (e.g. scans, laboratory values) will be provided upon request.

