13. STATISTICAL CONSIDERATIONS

13.1 Study Design/Endpoints

This is a phase I trial of the combination of dabrafenib, trametinib, and INCB039110 in patients with BRAF-mutant advanced solid tumors. The primary objective of the study is to determine the maximum tolerated dose (MTD) of the combination; secondary objectives will provide preliminary estimates of efficacy and toxicity. The escalation and stopping rules imply that the incidence rate for DLT will be less than 33% at the MTD. Following the identification of the MTD, up to an additional 20 patients will be enrolled in a dose expansion cohort at the MTD.

Toxicities and lab values will be graded according to the NCI Common Toxicity Criteria for Adverse Events (v4.0). Dose-limiting toxicities will be scored and will be defined as in Section 5.2.

Dose escalation will use a standard “3+3” approach, beginning in dose level 1, with dosing and rules for escalation and de-escalation described in the tables below. Tolerability assessments will be based on cycle 1 alone. The MTD is defined as the highest dose level at which 0 or 1 of six patients has experienced a DLT. If an excessive number of toxicities occur at the initial dose level 1, the dose will be reduced to the fall-back dose of -1. If dose level -1 has excessive toxicity, the study will stop.

Number of Patients with DLT at a Given Dose Level	Dose Escalation Rule
0 out of 3	Proceed to the next dose level and enroll 3 patients
1 out of 3	Enroll and treat 3 additional patients at this dose level
≥ 2 out of 3	Dose escalation will be stopped. The MTD will be one dose below this dose level. Three (3) additional patients will be entered at the next lower dose level if only 3 patients were treated previously at that dose.
1 out of 6	Proceed to the next dose level.
≥ 2 out of 6	Dose escalation will be stopped. The MTD will be one dose below this dose level. Three (3) additional patients will be entered at the next lower dose level if only 3 patients were treated previously at that dose.
If $\geq 2/3$ or $\geq 2/6$ patients at dose level 1 experience dose limiting toxicities, dose level -1 will be enrolled. If dose level -1 proves too toxic, the study will stop.	Dose escalation will be stopped. The MTD will be one dose below this dose level. Three (3) additional patients will be entered at the next lower dose level if only 3 patients were treated previously at that dose.

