The following table shows the probability of escalating the dose for various true, but unknown, rates of unacceptable toxicity.

True DLT Rate	Probability of Dose Escalation
0.10	0.91
0.20	0.71
0.30	0.49
0.40	0.31
0.50	0.17
0.60	0.08

A patient will be replaced if determination of DLT cannot be adequately assessed because of rapid disease progression or if treatment is stopped during the first cycle of therapy for reasons other than toxicity.

When the MTD had been determined, up to 20 patients will be enrolled in an expansion cohort of patients with melanoma to obtain preliminary toxicity and efficacy estimates. Patients treated at the MTD during the dose escalation phase may be included in the expansion cohort. Toxicity and efficacy rates will be summarized with 90% exact binomial confidence intervals.

The table below summarizes the probabilities of observing at least one patient with a severe or unexpected toxicity in the expansion cohort for a range of incidence rates.

True Incidence of Unexpected or Severe Toxicity	Probability of Observing One or More Patients with Toxicity among 20
0.01	0.18
0.03	0.46

True Incidence of Unexpected or Severe Toxicity	Probability of Observing One or More Patients with Toxicity among 20
0.05	0.64
0.08	0.81
0.09	0.85
0.10	0.88
0.15	0.96

Secondary endpoints that will be assessed for the 20 patients treated at the MTD in the dose-expansion cohort are: objective response rate, progression-free survival (PFS), 6-month PFS, and 1-year overall survival (OS).

Objective response rate is defined as the proportion of patients with complete or partial response as their best response to therapy. At the time of each restaging, patients will be classified as achieving complete response (CR), partial response (PR), stable disease (SD), progressive disease (PD), or non-evaluable for response according to RECIST (Version 1.1) criteria. Objective response will be determined by the best overall response designation recorded between the date of first dose of trial therapy and the date of objectively documented disease progression or cessation of trial therapy, whichever occurs first. For patients without documented progression or cessation of trial therapy, all available response designations will contribute to the objective response determination.

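### The expansion of up to 20 patients has no pre-specified toxicity boundary, and the 0–1 of 6 rule that names the MTD does not secure the claimed DLT rate below 33%

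*Combined protocol and SAP*

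**What the plan says.** Section 13.1 makes this claim for the dose that will be expanded: "The escalation and stopping rules imply that the incidence rate for DLT will be less than 33% at the MTD". The selection rule is "The MTD is defined as the highest dose level at which 0 or 1 of six patients has experienced a DLT", and "Tolerability assessments will be based on cycle 1 alone". The expansion is described as "Following the identification of the MTD, up to an additional 20 patients will be enrolled in a dose expansion cohort at the MTD". Later in the same section: "Patients treated at the MTD during the dose escalation phase may be included in the expansion cohort".

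The cohort-level DLT rules (Table 5.2 in Section 5.3, repeated in 13.1) concern escalation and de-escalation between dose levels. For the expansion, 13.1 gives a table introduced by "The table below summarizes the probabilities of observing at least one patient with a severe or unexpected toxicity in the expansion cohort", for incidences of 1% to 15%, and 90% exact binomial intervals.

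Oversight of the cohort comes from two places. Section 1.2 requires a review of PK and safety data before the expansion opens. Section 12.2 says: "The DSMC will review each protocol up to four times a year or more often if required to review toxicity and accrual data". The information given to the committee may include DLTs, and safety questions are taken up with the Overall PI and study team.

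**The concern.** The expansion is the first point at which the chosen dose is tested in more than six patients, so it is where a wrong choice would show. The plan does not say what number of DLTs would contradict the under-33% statement, when anyone would look, or whether expansion DLTs can reopen the MTD. At stake are the patients enrolled after such evidence has appeared, and the trial's ability to stand by its statement about the dose it names, which is its primary objective.

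**Working it through.** **Inputs.** MTD criterion, 33% claim, cohort size and both probability tables: Section 13.1. DLT window, days 1–28: Section 5.3. Accrual of 2–3 patients per month: Section 13.2. Below, p is the true DLT rate and q = 1 − p.

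**1. The plan's own figures reproduce.**
- Escalation probability, q³ + 3pq²·q³, gives 0.906, 0.709, 0.494, 0.309, 0.172 and 0.082 at p = 0.10 to 0.60. The plan prints 0.91, 0.71, 0.49, 0.31, 0.17 and 0.08.
- At least one event in 20, 1 − (1 − r)²⁰ at incidence r, gives 0.182 at 1% and 0.961 at 15%. The plan prints 0.18 and 0.96.

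**2. Chance that a dose meets the MTD criterion.** P(0 or 1 of 6) = q⁶ + 6pq⁵.

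| True rate | q⁶ | 6pq⁵ | Sum |
|---|---|---|---|
| 33% | 0.090 | 0.267 | 0.36 |
| 40% | 0.047 | 0.187 | 0.23 |
| 50% | 0.016 | 0.094 | 0.11 |

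The upper 90% exact limit is 39% after 0/6 (1 − 0.05^(1/6) = 0.393) and 58% after 1/6. Both exceed 33%.

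**3. Chance that the final MTD is this toxic.** This needs a dose-toxicity curve, which the documents do not give. Enumerating the whole 3+3, and assuming a top level at 0/3 is filled to six, gives these chances that the selected MTD has a true rate of 40% or more:

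| Assumed rates at levels −1, 1, 2, 3 | Probability |
|---|---|
| 10, 20, 30, 45% | 0.06 |
| 5, 10, 20, 40% | 0.15 |
| 10, 20, 40, 50% | 0.17 |
| 20, 40, 50, 60% | 0.24 |

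**4. Exposure without a boundary.** Twenty patients enrol in 20/3 = 6.7 to 20/2 = 10 months. If the committee met quarterly, 3 × 2 = 6 to 3 × 3 = 9 patients would enrol between meetings. Full enrolment gives 20 × 0.40 = 8 expected DLTs at a true 40%, and 10 at 50%. If the six escalation patients count towards the 20, new patients number about 14.

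**5. An illustrative boundary.** Pause at 3 or more of the first 5, 5 or more of the first 10, or 7 or more of the first 15, counting new expansion patients only. Exact calculation at p = 0.5:
- Pause at 5: P(X ≥ 3) = 16/32 = 0.500.
- Pause at 10: (1·1 + 5·6 + 10·16)/1024 = 191/1024 = 0.187.
- Pause at 15, by the same recursion: 0.097.
- Total 0.784; no pause 0.216.
- Mean patients over all runs: 5(0.500) + 10(0.187) + 15(0.097) + 20(0.216) = 10.1. Mean DLTs: half of that, 5.1.
- Among runs that pause: 7.4 patients and 4.4 DLTs.

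| True rate | 10% | 17% | 20% | 25% | 30% | 33% | 40% | 50% |
|---|---|---|---|---|---|---|---|---|
| P(pause) | 0.01 | 0.05 | 0.08 | 0.15 | 0.26 | 0.33 | 0.53 | 0.78 |

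**6. Who is counted matters.** The six patients who establish the MTD have at most 1 DLT by definition. If they enter the count first, the look at 5 cannot trigger, and the pause probability falls to 0.09 at 40% and 0.24 at 50%.

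**The case against.** The case against has four parts.

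- **Oversight exists.** The committee is independent of the study, may receive DLT information and can meet more often than quarterly. A PK and safety review precedes the expansion. Section 6 modifies dosing for individual patients, Section 7.2 sends serious events to the Overall PI, and Section 5.5 requires notice of life-threatening complications within 24 hours. All of this stands. A reader might infer that a too-toxic dose would necessarily be given to all 20 patients, or that only four looks a year are possible; the text supports neither. But none of these provisions links an observed expansion DLT rate to a pause, and the pre-expansion review cannot see expansion data.
- **The risk is easily overstated.** A reader might take 0.31 and 0.17 from the plan's table as the chance of naming a 40% or 50% dose as the MTD. The plan labels that table "The following table shows the probability of escalating the dose for various true, but unknown, rates of unacceptable toxicity", and it includes levels cleared at 0/3. The figures that match the MTD criterion are 0.23 and 0.11, and even these are conditional on the level being reached and on no higher level being chosen.
- **A boundary has a price.** Quoting only 5–8%, the cost at true rates of 17–20%, would hide the 0.26 at 30%, a rate that the plan's own statement accepts. This stands and must be disclosed.
- **The expansion is descriptive and any limits are a matter of choice.** This also stands. With patient-by-patient monitoring against a 33% null and at most 0.10 crossing probability there, detection is only 0.22 at 40% and 0.52 at 50%. That is a reason for the sponsor to choose the threshold and publish its properties, not a reason to have none.

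**Conclusion.** The point holds. The rules do not secure a DLT rate below 33% at the MTD: a dose at 33%, 40% or 50% meets the criterion with probability 0.36, 0.23 or 0.11. The expansion that follows has no pre-specified boundary, interim look or review trigger. The gap itself rests on the text alone. The probability of a final MTD at 40% or more, 0.06 to 0.24, rests on assumed curves and is only indicative. The boundary results assume independent patients, complete cycle 1 data at each look and a count restricted to new patients. Such a boundary reduces exposure to a wrongly chosen dose but does not remove it.

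**What to change.** Add a paragraph to Section 13.1 that:

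1. sets an enrolment-pause boundary for cycle 1 DLTs in the expansion, which triggers DSMC review before further enrolment and does not by itself end the trial;
2. applies it to newly enrolled expansion patients only;
3. states how patients still inside the 28-day DLT window are handled at each look, since at 2–3 per month about 2–3 more would enrol while a look is completed unless accrual is held;
4. reports pause probability and expected enrolment beside the existing tables, across true rates both below and above 33%.

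The limits in the working are an illustration; the threshold is for the sponsor to set. Section 13.1 should also reconcile its two statements on whether the 20 are all additional patients or may include those from escalation, and reword the 33% sentence so that it does not read as a guarantee. Section 12.2 should refer to the new trigger.

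The cost is one paragraph and one table. DLTs are already defined and the committee already exists. For the illustrated limits, the operational price is an unnecessary review with probability 0.05 at a true 17%, 0.08 at 20%, 0.15 at 25%, 0.26 at 30% and 0.33 at 33%.
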